Once volunteers have been screened, they will enter a 4-week pre-randomisation run-in period to exclude participants intolerant to taking liquid oil. All subjects will be instructed to take 15 ml daily of a similarly flavoured oil (citrus flavoured Sunola oil). While the exact contents of this preparation will not be revealed, it will be explained to participants that this preparation is designed to test common aspects of the interventions, but differs from the actual test oil preparations. A standardized instructional video demonstrating a method of taking liquid oil that enhanced tolerability by ‘layering’ on juice will be shown to all participants prior to run-in. Participants will be instructed to take the test oil on juice using the two glass technique [2]. Briefly, one of two shot glasses is filled with fruit juice and the other half filled with juice. The required dose of oil is then measured and layered onto the juice in the half filled glass. Without stirring, the contents are then swallowed in a single gulp. Immediately thereafter, the glass of juice alone is sipped slowly over a period of about 15 seconds. The oil and juice is taken with a meal and not on an empty stomach. Carbonated drinks are avoided. The oil can be taken in divided doses. This method has generally been effective in avoiding a ‘repeating’ fish oil taste.

Patients will be reviewed in the 3rd week after commencing the run-in oil. Subjects who do not attend the appointments or are non-compliant (who consume less than 75% of the oil as assessed by volume) or are intolerant of the oil will not be randomised. The requirements

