High dose fish oil contains EPA 18% and DHA 12%, supplying 4.5g EPA+DHA per day. The low dose comparator oil, a blend of fish oil and high oleic sunola oil in a ratio of 1:9, supplies 0.45g EPA + DHA per day, which is equivalent to 1.5 standard 1g fish oil capsule daily. Both oils are flavoured with citrus oils and will be provided in identical dark 500mL bottles. Fish oil is sourced from Berg LipidTech Aalesund, Norway. The oils, blending, masking and bottling is performed by Melrose Health, Victoria, Australia. Study oil bottles will be returned at each study visit and volume of unconsumed oil measured to assess compliance. The presence of fish oil in the comparator will obviate the ethical problem of denying patients n-3 fatty acids that are recommended for cardiovascular health and will also add 'fishy' sensate properties that will militate against unmasking. We have previously shown addition of citrus flavouring to fish oils and vegetable oils achieves masking. The EPA and

DHA dose in the undiluted test fish oil has been shown to have anti-inflammatory effects in a variety of clinical settings, whereas the comparator oil will deliver a dose of fish oil that is well below the minimum amount (10ml/d) that has been associated with anti-inflammatory effects in RCTs. Participants will be provided with paracetamol (500mg) tablets with instructions that they could safely use up to 8 per day.

Participants will undergo assessments at baseline, 6 weeks, 3, 6, 9, 12, 18 and 24 months with interim phone calls to participants to encourage continuing compliance and participation

Dietary and general advice:

Subjects will be instructed to use olive oil based products (spreads, cooking oils, dressings etc), where possible, to minimise variation in consumption of n6 polyunsaturated fatty acids which compete with dietary n3 fatty acids. Written instructions regarding technique for taking the oil and directions for the background diet will be provided. All participants will also be given written information on knee osteoarthritis and generic instructions regarding exercises appropriate for maintaining knee function in OA and general fitness. The package of informed consent and written advice will include information regarding potential unwanted effects of fish oil and paracetamol.

COMPLIANCE

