The degree of compliance with test oils will be measured in two ways: (i) calculation of consumed fish oil by count of bottles provided and measurement of oil remaining in returned partly used bottles and (ii) fasting plasma omega-3 fatty acid analysis. These assessments will be undertaken at 3, 6, 12, 18 and 24 months. The plasma fatty acid analysis results will not be available to subjects or investigators till the completion of the study.

OUTCOME MEASURES

Primary outcomes:

1. Pain (WOMAC NRS 3.1 index [4], 10 point numerical scale) at 3, 6, 9, 12 and 24 months (knee specific)
2. Change in knee MRI cartilage volume at 2 yrs.

Secondary outcomes:

1. Disability (WOMAC NRS 3.1 index [4], 10 point numerical scale) at 3, 6, 9, 12 and 24 months (knee specific)

2. Quality of life (AQOL) [5]
3. Analgesic use, measured using a daily diary (NSAID) and paracetamol (pill count at each visit)
4. Change in MRI scores of bone marrow lesions at 2 years
5. Safety assessments/adverse events

In addition to the designated outcome measures, blood pressure, full blood count and electrolytes and liver function testing, presence of comorbidities (eg renal disease, cardiovascular disease, peptic ulcer disease) and a diet questionnaire, DQES V2[6], used to assess n-3 and n-6 fatty acid intake in usual diet, will be assessed at baseline.

As the study will extend over two years in a population at an age at risk for cardiovascular disease and declining bone density, routine investigations will be undertaken at baseline and two years to monitor collateral health effects and risks including:

1. fasting blood lipids
2. low titre c-reactive protein
3. bone mineral density of hip and spine
4. lung spirometry (The Queen Elizabeth Hospital participants only)

The assessment schedule is summarized in Table 1, and data collection forms are presented in Appendix 1.

Table 1. Schedule of assessment for primary and secondary outcome measures

FOSTAR STUDY ASSESSMENTS									
	Enrolment	Randomisation	Treatment						Completion
	Visit 1 (~4 weeks)	Visit 2 (0 weeks)	Visit 3 (3 month)	Visit 4 (6 month)	Visit 5 (9 month)	Visit 6 (12 month)	Visit 7 (18 month)	Visit 8 (24 month)	
Informed Consent for FOSTAR	X								
Medical History	X								
Surgical History	X	X	X	X	X	X	X	X	
OA History		X							
Inclusion/Exclusion Criteria	X	X							
Concomitant medications	X	X	X	X	X	X	X	X	
Physical Exam/Vital Signs	X	X	X	X	X	X	X	X	
Fish Oil Dosing DVD	X	X							
Run-In Fish Oil	X								

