Has the take home diary been supplied and explained?		
Has the subject been supplied with analgesic medication for pain relief?		
Make sure the details of this are recorded on the Paracetamol Accountability Sheet		

Site Number:

Randomisation Number:

Subject Initials:

Study Selected Knee:

FOSTAR STUDY

Visit 2 (0 months) - RANDOMISATION

Visit Date.....					  /   /    	DD / MM / YYYY			

KNEE X-RAY									
YES NO									
If not available at Visit 1, has an x-ray (no older than 12 months) of the study selected knee been assessed by the PI									
Does the subject meet knee inclusion criteria									
1. Less than Grade – 4 changes in their study selected knee									
2. An osteophyte on x-ray									
And at least one of the following:									
- knee age greater than 50 years									
- stiffness lasting less than 30 minutes									
- crepitus									

STUDY SELECTED KNEE									
LEFT RIGHT									
This subject's Study Selected knee is their									
									

Site Number:

Randomisation Number:

Subject Initials:

Study Selected Knee:

RUN-IN FISH OIL	
YES	NO
Was the run-in oil well tolerated?  	
If not, describe the symptoms below:	
Any adverse events recorded here or in take-home diary to be transcribed to Adverse Events Record	
Has the run-in oil been returned  	
Volume of the returned bottle mL	
% of returned oil % (% = amount returned/amount supplied x 100)	
Was at least 75 % of expected run-in fish oil consumption confirmed?  	
Was tolerance and compliance adequate?  	
If no, withdraw subject	
If yes, continue with visit.....	

ANALGESIC USE	
YES	NO
Has subject withheld taking anti-inflammatory and analgesic medications prior to appointment  	
If YES, continue with questionnaires.	
If NO, ask subject to withhold analgesic and inflammatory	

Site Number:

Randomisation Number:

Subject Initials:

Study Selected Knee:

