Blood Pressure(sitting, after resting for 5 minutes)	mmHG

STUDY FISH OIL	
	YES NO
Has the Visit 2 fish oil been returned (inc. any empty bottles)	 
How many mLs are remaining?mL	
What percentage of expected was taken?% (=amount actually taken/amount expected to be taken x 100)	
We want at least 75% compliance so if necessary, encourage subject to keep taking the fish oil on a daily basis	
Has Visit 3 fish oil been explained and supplied	 

VISIT 2 DIARY	
	YES NO
Has the subject's Visit 2 diary been collected and reviewed	 
Have all diary concomitant medication records been transcribed into the CRFs Concomitant Medication Section	 
Have all diary adverse event records been transcribed into the CRFs Adverse Events Section	 

PREPARATION FOR NEXT APPOINTMENT	
	YES NO
Has an appointment been made for the subjects next appointment in	 

Site Number:

Randomisation Number:

Subject Initials:

Study Selected Knee:

3 months time	
Details:/...../.....am/pm DD/MM/YYYY	
Has the subject been supplied an IMVS form for fasting bloods prior to next visit	 
Has a Visit 3 take home diary been supplied and explained	 
Has the pedometer issued at Visit 2 been collected and the information recorded in the Pedometer Record section	 
Has the subject been issued with Analgesic medication to use for pain relief	 
Please record this information on the Analgesic Medication Form	

Site Number:

Randomisation Number:

Subject Initials:

Study Selected Knee:

FOSTAR STUDY

Visit 4 (6 months) - TREATMENT

Visit Date..... / / DD / MM / YYYY

ANALGESIC USE		
	YES	NO
Has subject withheld taking anti-inflammatory and analgesic medications prior to appointment If YES, continue with questionnaires. If NO, ask subject to withhold analgesic and inflammatory medications from today and complete questionnaires at home. The questionnaires are then to be returned in pre-paid envelopes.		

QUESTIONNAIRES					
	Supplied		Completed		
	YES	NO	YES	NO	

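### On the forms shown, no visit after randomisation asks how the study oil was tolerated, the take-home diary is the only stated feed to the adverse event section, and the 6-week assessment has no schedule column or form

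*Supplement*

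**What the plan says.** The protocol's Outcome Measures section lists "Safety assessments/adverse events" as the fifth secondary outcome. The protocol body does not say how events are elicited, when, or how they are analysed. Neither Table 1 nor the Appendix 1 schedule has an adverse event row.

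The Run-in Period section describes the run-in oil as citrus-flavoured Sunola and says that it "differs from the actual test oil preparations". At Visit 2 the form asks "Was the run-in oil well tolerated", provides space for symptoms, and instructs: "Any adverse events recorded here or in take-home diary to be transcribed to Adverse Events Record". At that visit, then, both a direct answer and the diary feed the record.

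At Visits 3 to 8 the study-oil block asks whether bottles were returned, how much remains and what percentage was taken. It reminds staff of the 75% compliance target and, except at Visit 8, checks that new oil was supplied. The diary block asks "Have all diary adverse event records been transcribed into the CRFs Adverse Events Section". Other blocks ask about new diagnoses, medication changes and hospital procedures.

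On timing, the Intervention section says "Participants will undergo assessments at baseline, 6 weeks, 3, 6, 9, 12, 18 and 24 months", and adds interim phone calls meant to support adherence and retention. Both schedules and the forms go from Visit 2 at week 0 to Visit 3 at 3 months.

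**The concern.** The trial compares 4.5 g with 0.45 g of EPA+DHA a day, so how well the higher dose is tolerated is a natural question for its readers. A direct tolerance question with a route into the adverse event record exists, but it is put only about an oil that neither arm receives. It is not carried forward to the oils under test.

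After randomisation, a symptom that leads to no diagnosis, hospital visit or medication change has one stated way into the adverse event section: the participant writes it in the diary, returns the diary, and staff transcribe it. The forms name no fallback if the diary is missing. The protocol's own example of an unwanted effect, the repeating taste of fish oil, is of this kind. At stake is whether the trial can detect a difference in mild tolerability, or whether a finding of no difference partly reflects weak recording.

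**Working it through.** **1. Routes into the adverse event section, as shown on the forms**

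| Source | Visit 2 | Visits 3 to 8 |
|---|---|---|
| Direct question on oil tolerance | Yes, run-in oil; routed to the adverse event record | None |
| Take-home diary | Routed to the adverse event record | Routed to the adverse event section |
| New medical conditions | Asked; points to the concomitant medications record | Same |
| Hospital procedures | Asked; no onward route stated | Same |
| Medication changes | Asked; points to the concomitant medications page | Same |

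The last three rows do not depend on diary return. They should pick up diagnosed, treated or serious events, but would probably miss undiagnosed taste, reflux or gut symptoms.

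**2. Length of the diary windows**

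Between successive forms from Visit 2 to Visit 8 the intervals are 3, 3, 3, 3, 6 and 6 months (total 24).

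**3. Effect of under-recording**

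The plan gives no figure for adverse event rates, diary return or power on this outcome, so there is nothing to reproduce. The 100 per group is taken from the Sample Size Consideration section. The event rates and the recorded fraction are assumptions.

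Let p1 and p2 be the true proportions of participants with an event, and s the fraction recorded, the same in both arms. The recorded rates are s·p1 and s·p2. The difference becomes s(p1 − p2), and the ratio is unchanged.

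The approximate two-sided 5% power, with P1 = s·p1, P2 = s·p2 and P̄ their mean, is

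Φ{ [ (P1 − P2) − 1.96·√(2P̄(1 − P̄)/n) ] / √([P1(1 − P1) + P2(1 − P2)]/n) }, with n = 100.

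For p1 = 0.30, p2 = 0.15, s = 1:
- P̄ = 0.225, null standard error √(2 × 0.225 × 0.775/100) = 0.0591.
- Alternative standard error √((0.21 + 0.1275)/100) = 0.0581.
- Φ[(0.15 − 1.96 × 0.0591)/0.0581] = Φ(0.59) = 0.72.

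| Assumed true rates | All recorded | 75% recorded | 50% recorded |
|---|---|---|---|
| 30% v 15% | 0.72 | 0.57 | 0.39 |
| 20% v 10% | 0.51 | 0.39 | 0.27 |

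These figures ignore attrition, which would lower them further.

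**4. The 6-week assessment**

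- Intervention text: 6 weeks, 3, 6, 9, 12, 18 and 24 months, which is 7 post-baseline assessments.
- Table 1, the Appendix 1 schedule and the forms: Visits 3 to 8, which is 6.
- Sample Size Consideration: six treatment visits, which matches Visits 3 to 8.

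On the forms, the first scheduled on-treatment visit is therefore at 3 months, about 52/4 = 13 weeks, and not at 6 weeks.

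**The case against.** The strongest reply is that the diary and the adverse event section of the case report form are cited but not reproduced. Either could hold structured tolerability items, and the line about transcribing diary entries does not say that the section accepts nothing else. This stands, and it limits the point to the forms shown. Items in the diary would still depend on its return.

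Secondly, safety information does not come from the diary alone. Every post-randomisation visit asks directly about new conditions, hospital procedures and medication changes, and records weight and blood pressure. Phone calls are planned, so 3 months is the first scheduled visit and not necessarily the first contact. This also stands. It confines the gap to mild symptoms, though these items are not linked to the adverse event section and the calls have no stated safety purpose.

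Thirdly, using a different oil in the run-in is not a fault. It screens for intolerance of liquid oil, and the protocol discloses that it differs from the test oils.

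A reader might go further and infer that the high-dose arm would lose more events, biasing the comparison between arms. The documents do not support that. Both arms take the same volume, from identical bottles with the same flavouring, and use the same forms. No diary-return or unblinding figure is given. Even if people who dislike the oil return fewer diaries, that would apply in both arms: with an assumed 20% v 15% and a common 70% return, the recorded rates are 0.20 × 0.70 = 14.0% and 0.15 × 0.70 = 10.5%, and the ratio stays at 1.33. Bias in that ratio needs recording that differs by arm, which is speculation here.

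**Conclusion.** The point holds for the forms as shown. No post-randomisation form asks about tolerance of the study oil, the diary is the only stated feed to the adverse event section, and the direct questions on diagnoses, hospital procedures and medication changes are not tied to it. The likely consequence is under-recording of mild, undiagnosed symptoms, which shrinks the absolute difference and costs power. Its size depends on event rates and a recorded fraction that the documents do not give; the power figures illustrate it and do not estimate it.

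The primary outcomes are untouched, and uneven recording by arm is not shown. This is a cheap improvement to a stated secondary outcome.

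The 6-week assessment is a separate, plain inconsistency: it appears only in the Intervention text. No listed pain or disability time point uses it, and it adds nothing to the argument about adverse events.

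**What to change.** 1. In the study-oil block at Visits 3 to 8, repeat the Visit 2 tolerance item, reworded for the study oil: *Since the last visit, has the study oil been well tolerated? Yes / No. If no, give the symptoms and enter them in the Adverse Events Record.* Ask every participant in both arms, whether or not the diary is returned.
2. State on the form that new medical conditions and hospitalisations are also entered in the adverse event record.
3. In the protocol, state that adverse events are summarised by arm from this question, the diary and the visit items together. Report diary return by arm, which the existing diary check box can supply, so that a reader can judge whether recording was even.
4. Reconcile the 6-week assessment in the Intervention section with Table 1, the Appendix 1 schedule, the forms and the six treatment visits in the sample-size section, so that all give the same visits.

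The first change is one repeated item per visit, about a minute of coordinator time, with no extra procedure. The downside is more minor events to record in both arms. The remaining changes are edits to text, forms or schedule. If the diary or adverse event section already holds a structured tolerance item, the protocol should say so; asking it at the visit would still remove the dependence on diary return.
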